For this “Notable Laboratory Values” analysis, *all* laboratory values after randomization will be taken in account, i.e., any values obtained after Day 1, at unscheduled visits, as well as values from the regularly scheduled laboratory visit at Month 12. Three Notable Laboratory Values tables and accompanying by-subject listings will be presented: (1) notable abnormalities for subjects with normal Baseline results, (2) notable abnormalities for subjects with abnormal Baseline results and (3) notable abnormalities without regard to Baseline abnormalities (i.e., normal or abnormal Baseline results). The table without regard to Baseline abnormalities will be a composite of the previous two tables (normal Baseline, abnormal Baseline).

CONFIDENTIALLab analytes and primary criteria used for Notable Laboratory Values:

a. HEMATOLOGY

- i. Hemoglobin $< 0.75x$ Baseline
- ii. Platelets < 75 or > 750 ($10^9/L$)
- iii. WBC count < 2.5 or > 17.5 ($10^9/L$)
- iv. Neutrophils (absolute) $< 0.5xLLN$ or $> 1.5xULN$
- v. Eosinophile (absolute) $> 1.5xULN$
- vi. Lymphocytes (absolute) $< 0.5xLLN$ or $> 1.5xULN$

b. LIVER FUNCTION

- i. Total bilirubin $> 1.5xULN$
- ii. Alkaline phosphatase $> 1.5xULN$
- iii. ASAT (SGOT) $> 3xULN$
- iv. ALAT (SGPT) $> 3xULN$
- v. GGT $> 3xULN$

c. RENAL FUNCTION

- i. BUN $> 1.3xULN$
- ii. Creatinine $> 1.3xULN$

d. ELECTROLYTES

- i. Potassium $< 0.9xLLN$ or $> 1.1xULN$
- ii. Sodium $< 0.9xLLN$ or $> 1.1xULN$
- iii. Chloride $< 0.9xLLN$ or $> 1.1xULN$
- iv. Carbon Dioxide $< 0.9xLLN$ or $> 1.1xULN$
- v. Calcium $< 0.9xLLN$ or $> 1.1xULN$
- vi. Phosphorus $< 0.9xLLN$ or $> 1.1xULN$

Notable abnormalities for subjects with abnormal Baseline results are subject to the primary criteria above and the following secondary criteria:

a. HEMATOLOGY

- i. Hemoglobin $< 0.75x$ Baseline (same as primary criterion)
- ii. Platelets $< 0.75x$ Baseline or $> 1.25x$ Baseline

CONFIDENTIAL

- iii. WBC count $< 0.75x$ Baseline or $> 1.25x$ Baseline
- iv. Neutrophils (absolute) $< 0.5x$ Baseline or $> 1.5x$ Baseline
- v. Eosinophils (absolute) $> 1.5x$ Baseline
- vi. Lymphocytes (absolute) $< 0.5x$ Baseline or $> 1.5x$ Baseline

b. LIVER FUNCTION

- i. Total bilirubin $> 1.5x$ Baseline
- ii. Alkaline phosphatase $> 1.5x$ Baseline
- iii. ASAT (SGOT) $> 1.5x$ Baseline
- iv. ALAT (SGPT) $> 1.5x$ Baseline
- v. GGT $> 1.5x$ Baseline

c. RENAL FUNCTION

- i. BUN $> 1.3x$ Baseline
- ii. Creatinine $> 1.3x$ Baseline

d. ELECTROLYTES

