- i. Potassium $< 0.9x$ Baseline or $> 1.1x$ Baseline
- ii. Sodium $< 0.9x$ Baseline or $> 1.1x$ Baseline
- iii. Chloride $< 0.9x$ Baseline or $> 1.1x$ Baseline
- iv. Carbon dioxide $< 0.9x$ Baseline or $> 1.1x$ Baseline
- v. Calcium $< 0.9x$ Baseline or $> 1.1x$ Baseline
- vi. Phosphorus $< 0.9x$ Baseline or $> 1.1x$ Baseline

ECG

ECG results will be tabulated as “normal” or “abnormal” at each visit, and will be presented in a normal/abnormal shift table between Baseline and each scheduled ECG visit, as well as between Baseline and the last ECG taken. Descriptive statistics will be presented for continuous variables (eg, heart rate and RR, PR, QRS, QT, QTcB and QTcF intervals) at each visit. A by-patient listing will be provided for ECGs which are deemed abnormal.

[figure not shown]

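### For patients with an abnormal baseline, the notable-laboratory rule can count a still-abnormal value that has improved, while passing over one that is unchanged or moderately worse

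*SAP*

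**What the plan says.** The rule is in the Year 1 SAP under Clinical Laboratory Determination and is repeated in section 4.3.6 of the Year 2 SAP. A primary list sets limits for 19 analytes, mostly fixed values or multiples of the reference limits. For patients whose baseline was already abnormal, a second list of multiples of baseline is added: "Notable abnormalities for subjects with abnormal Baseline results are subject to the primary criteria above and the following secondary criteria".

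For ten analytes both lists are two-sided. Platelets have primary limits of 75 and 750, and the secondary entry is "Platelets $< 0.75x$ Baseline or $> 1.25x$ Baseline". Potassium has primary limits of 0.9 x LLN and 1.1 x ULN, and the secondary entry is "Potassium $< 0.9x$ Baseline or $> 1.1x$ Baseline"; the other five electrolytes have the same form. WBC, neutrophils and lymphocytes are also low-or-high in both lists.

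Eosinophils, the five liver analytes and the two renal analytes have upper limits only. Hemoglobin has one criterion, a value below 0.75 x baseline, which serves in both lists.

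The flags feed a table for abnormal-baseline patients, a composite table that also takes in the normal-baseline table, and by-subject listings. No visible sentence in either SAP pairs a low breach with a low change, or a high breach with a high change.

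**The concern.** The evident use of a limit relative to baseline is to separate a new deterioration from an abnormality that was already present. When both criteria are two-sided and unpaired, a patient can meet the primary criterion on the low side because the value is still low, and the secondary criterion on the high side because the value has risen. The same can happen in mirror image at the high end.

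The abnormal-baseline and composite tables would then mix partial improvements with deteriorations, and a reader of an incidence count could not tell them apart. Because the stratum of patients with an abnormal baseline is likely to be small, even one or two such entries could be a visible share of it.

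**Working it through.** **Inputs.** The limits and multiples are those in the Year 1 SAP lists. The documents give no incidence for this rule and no reference ranges, so there is no figure of the plan's own to reproduce. Results for analytes tied to a reference limit are given as multiples of LLN or ULN, which need no assumption.

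**Count.** Analytes: 6 hematology + 5 liver + 2 renal + 6 electrolytes = 19. Two-sided in both lists: 4 + 6 = 10.

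**Algebra.** Let L and H be the low and high primary limits, a < 1 < c the secondary multiples, b the baseline and v the later value. There are two opposite-direction flags:

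- v < L and v > c·b. Then b < v < L, so the value has risen towards normal. This requires b < L/c.
- v > H and v < a·b. Then b > v > H, so the value has fallen towards normal. This requires b > H/a.

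Every opposite-direction flag is therefore a move towards normal by a value still beyond the primary limit. A value inside the primary limits fails the primary criterion and is never flagged.

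**Baselines needed.**

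| Analyte | Low baseline, b < L/c | High baseline, b > H/a |
|---|---|---|
| Platelets | 75/1.25 = 60 | 750/0.75 = 1000 |
| WBC | 2.5/1.25 = 2.0 | 17.5/0.75 = 23.3 |
| Neutrophils, lymphocytes | 0.5/1.5 = 0.333 x LLN | 1.5/0.5 = 3.0 x ULN |
| Each electrolyte | 0.9/1.1 = 0.818 x LLN | 1.1/0.9 = 1.222 x ULN |

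**Examples.**

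- Platelets, baseline 50. Limits: below 75, and either below 0.75 x 50 = 37.5 or above 1.25 x 50 = 62.5. A fall to 40 is not flagged, 50 unchanged is not flagged, and a rise to 70 is flagged. A larger fall, to 35, is flagged, as it should be.
- WBC, baseline 26. Limits: above 17.5, and either below 0.75 x 26 = 19.5 or above 1.25 x 26 = 32.5. A rise to 30 is not flagged, 26 unchanged is not flagged, and a fall to 18 is flagged.
- WBC, baseline 20. A fall to 14 is not flagged (inside 2.5 to 17.5). A fall to 17.6 is not flagged (not below 0.75 x 20 = 15).
- Potassium, baseline 2.6, assuming LLN 3.5 mmol/L. A fall to 2.4 is not flagged (above 0.9 x 2.6 = 2.34). A rise to 3.0 is flagged (below 0.9 x 3.5 = 3.15 and above 1.1 x 2.6 = 2.86). The flag at 3.0 occurs for any LLN above 3.0/0.9 = 3.33.

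**Plausibility.** With assumed ranges of 135–145 for sodium and 98–107 for chloride (mmol/L), the baselines needed are sodium below 110 or above 177, and chloride below 80 or above 131. For these two analytes the gap is mostly formal.

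**With matched direction.** A value below L cannot be both below a·b and above c·b, and likewise above H, so every flag is either matched or opposite. Requiring a match removes exactly the opposite flags for all 10 analytes and no flag for worsening.

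**Hemoglobin.** Its only criterion is v < 0.75·b. A baseline of 20 g/dL falling to 14.9 is flagged, since 0.75 x 20 = 15.0, although 14.9 lies inside an assumed adult range of 12–17. Direction matching does not touch this.

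**The case against.** A platelet count of 70 or a potassium of 3.0 still breaches the SAP's own primary limit, and neither SAP says that the abnormal-baseline table is meant to show worsening alone. On that view these are legitimate entries. It is true that the purpose is inferred and that such values are partial improvements, not recoveries. But a table meant to show every markedly abnormal value would also include the unchanged 50 and the 40, and the rule leaves both out. No sensible purpose yields that ordering.

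Both lists give the low limit before the high one, so a programmer might pair them naturally. That is possible, but it is not in the text. Reading the two lists as alternatives makes matters worse: any value still beyond its primary limit would then count, so an improving value could be flagged for all 19 analytes (ALT falling from 5 to 4 x ULN, for instance).

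The listings show all values of the analyte for each flagged patient, and changes from baseline are tabulated, so a reviewer can see the direction case by case. This stands as mitigation, but it does not correct the counts in the tables.

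A reader might infer that any value improving towards normal is counted for 10 of the 19 analytes. The documents do not support that: the primary limit must still be breached, from a baseline beyond the thresholds above. Nor do they support a claim that the comparison of arms is distorted. The tables are descriptive, and no test, endpoint or decision rule depends on them.

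**Conclusion.** The gap is real and small. As written, both SAPs can count a still-abnormal but improving value as notable for the 10 two-sided analytes, while an unchanged or moderately worse value is not counted. This follows from the stated limits alone, taking the two lists as jointly required.

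The number of patients cannot be computed, because the documents give no distribution of baseline laboratory values. Given the baselines required, it is probably few and may be none. The effect reaches only the abnormal-baseline table, the composite table and the listings; efficacy results are untouched. Hemoglobin is a separate route to a similar result, so under the rule as written 11 of the 19 analytes can flag a value that has moved towards normal.

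**What to change.** State in the SAP that, for patients with an abnormal baseline, the secondary criterion must be met in the same direction as the primary criterion: low limit with the lower multiple of baseline, high limit with the upper one. The Year 1 analysis has already been done according to the Year 2 SAP's introduction. The practical place is therefore section 4.3.6 of the Year 2 SAP, whose notable-value tables cover values from after Day 1, with a footnote to the Year 1 tables.

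Separately, decide and record how hemoglobin is to be handled for patients with a high baseline, or footnote that a flag can represent a fall from a high value.

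The cost is a sentence and a small programming change. The one downside is that some values that are improving but still markedly abnormal leave the notable-value tables; they remain in the full laboratory listings.

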4.1. General Considerations.....	11
4.1.1. Visit Windows	11
4.1.2. Handling Missing Data in Efficacy Analyses	11
4.1.3. Handling Missing Data in Descriptive Analyses.....	11
4.1.4. Handling Missing or Partially Missing Dates.....	12
4.1.5. CCI	12
4.1.6. Disposition of Subjects	12
4.1.7. Treatment Misallocation	13
4.1.8. Protocol Deviations.....	13
4.1.9. Demographic and Baseline Characteristics	13
4.1.10. Prior and Concomitant Medications	14
4.2. Efficacy Analysis.....	15
4.2.1. Mean GA growth (slope): EM, EOM vs. Sham.....	15
4.2.2. Time to Vision Loss Analysis.....	17
4.2.3. Other Secondary Endpoints	18
4.3. Safety Analyses.....	19
4.3.1. Extent of Exposure.....	19
4.3.2. Adverse Events	19
4.3.3. Serious Adverse Events	20
4.3.4. Vital Signs.....	21
4.3.5. Ophthalmic Variables	21
4.3.6. Clinical Laboratory	22
4.3.7. ECG.....	24
4.4. Other Analyses.....	25
4.4.1. Subgroup.....	25
4.5. Changes to Protocol-planned Analyses	25
5. Supporting Documentation.....	26
5.1. CCI	26
5.2. Statistical Analysis Plan Addendum for Cumulative Year 2 Data	27
6. References.....	28

Version History

SAP version	Date	Change	Rationale
2.0	22 June 2023	
 • Analysis populations and Expand analysis visit windows up to year 2 • Untransformed response outcome (growth rate of GA) without square root transformation will be used • Remove the per-protocol analysis • Revise the MMRM model to fit the design for year 2 analysis • Revise analysis on fellow eye (FE) • Vision loss analysis 	
Population at the re-randomization is defined. Analysis visit windows are defined to cover visits up to year 2 in the analysis data sets
 
Untransformed data is direct and easy to interpret the growth of GA area
 
Intent-to-treat population is the primary analysis set. Per-protocol analysis set doesn't provide additional meaningful information in this superiority study
 
With re-randomization at the end of year 1, the stratification factors from the initial randomization are no longer applicable to the cumulative data at year 2. In addition, the untransformed GA area will be used in the model. Several sensitivity analyses are added.
 
The study is on the study eye (SE) for efficacy and safety evaluation. FE will not provide additional information
 
Time-to-event analysis is added with the vision loss event defined as $BCVA \geq 15$ letters loss from baseline in 2 or more consecutive visits

1.0	3 August 2022		Original version: a brief SAP addendum for year 2 analysis

List of Abbreviations

Abbreviation	Term
AE	Adverse Event
AMD	Age-Related Macular Degeneration
ACP	Avacincaptad Pegol
ATC	Anatomic Therapeutic Chemical
BCVA	Best Corrected Visual Acuity
BUN	Blood Urea Nitrogen
CI	Confidence Interval
ECG	Electrocardiogram
ECOG	Eastern Cooperative Oncology Group
ETDRS	Early Treatment Diabetic Retinopathy Study
FA	Fluorescein Angiography
FAF	Fundus Autofluorescence
FP	Fundus Photography
GA	Geographic Atrophy
GGT	Gamma-glutamyl Transferase
ICH	International Conference on Harmonization
DSMB	Data Safety Monitoring Board
IOP	Intraocular Pressure
ITT	Intention-to-Treat
LLN	Lower Limit Normal
MAR	Missing at Random
MedDRA	Medical Dictionary for Regulatory Activities
MMRM	Mixed Model for Repeated Measures
MNAR	Missing Not At Random
NA	Not Available / Not Applicable
OU	Oculus Uterque (Both Eyes)
PSC	Posterior Subcapsular Cataract
REML	Restricted Maximum Likelihood
CCI	
SAE	Serious Adverse Event
SAP	Statistical Analysis Plan
SD	Standard Deviation
SE	Study Eye
SGOT/AST	Aspartate Aminotransferase
SGPT/ALT	Alanine Aminotransferase
ULN	Upper Limit Normal

VA	Visual Acuity
WBC	White Blood Cells
WHO	World Health Organization

1. Introduction

This Statistical Analysis Plan (Year 2) describes the statistical methodology and data handling of Year 2 for the clinical trial with Protocol Number: ISEE2008 (GATHER2), Version Date: 18 December 2020.

The trial consists of a total treatment period of 24 months. This SAP covers the final analyses to be performed on Year 2 cumulative data including visits at 18 and 24 months. The primary analysis on year 1 was conducted and documented separately in the SAP for the primary analysis.

At the end of year 1, patients receiving monthly ACP 2 mg will be re-randomized at Month 12 in a 1:1 ratio to the following treatment groups (denoted as EM or EOM):

- EM: ACP 2 mg administered monthly from Month 12 - Month 23
- EOM: Sham administered at Months 12, 14, 16, 18, 20, and 22, and ACP 2 mg administered every other month at Months 13, 15, 17, 19, 21, and 23

The name Zimura was used previously in the protocol and other document. Moving forward, a scientific name ACP will be used instead.

A final analysis of the double-masked phase of the study, including all double-masked data will be performed when all participants have completed the Month 24 visit or discontinued earlier.

A brief SAP addendum (version 1.0) for cumulative Year 2 data of ISEE2008 study was approved on 3 August 2022 before the unmasking of Year 1 data for primary analysis. The addendum prespecified mainly sequential statistical testing procedure on Year 2 (Supporting Document).

The purpose of this SAP (Year 2) is to expand the addendum to provide technical details for the Year 2 and the final analysis of the study.

1.1. Objectives and Endpoints

Efficacy objectives and corresponding Endpoints are tabulated below

Efficacy objectives	Endpoints

 • Demonstrate ACP 2mg in EM or EOM intravitreal injection after re-randomization reduces GA growth (slope) compared to Sham in patients with geographic atrophy secondary to age-related macular degeneration (AMD) up to Year 2. • Demonstrate ACP 2mg intravitreal injection reduces rate of persistent vision loss (BCVA) compared to Sham up to Month 24 	
 • GA area measured by FAF in 5 time points: Baseline, Month 6, Month 12, Month 18, and Month 24. • Time to vision loss (defined as BCVA loss \geq 15 letters from baseline at two or more consecutive visits up to Month 24).

 • [REDACTED] CCI [REDACTED] 	
 • [REDACTED] • [REDACTED] • [REDACTED]

Safety
	

 • Safety of ACP 2mg in EM or EOM intravitreal injection compared to Sham in patients with geographic atrophy secondary to age-related macular degeneration (AMD) up to Year 2. • Safety of ACP 2mg intravitreal injection compared to Sham in patients with geographic atrophy secondary to age-related macular degeneration (AMD) up to Year 2. 	
 • Adverse events (AEs) • Serious adverse events (SAEs) • Vital signs (pulse, systolic and diastolic blood pressure) • Ophthalmic variables (ophthalmic examination, best corrected visual acuity (BCVA), low luminance BCVA (LLBCVA), intraocular pressure (IOP)) • Electrocardiography (ECG) • Laboratory variables (blood: hematology, renal function, hepatic function, and electrolytes; urinalysis)

1.2. Study Design

Approximately 400 patients will be randomized at Day 1 in a 1:1 ratio to the following monthly treatment groups:

- ACP 2 mg
- Sham

[figure not shown]
Patients receiving monthly ACP 2 mg will be re-randomized at Month 12 in a 1:1 ratio to the following treatment groups: EM or EOM as described above. ACP 2mg denotes the treatment group from the initial randomization.

All patients who were initially randomized to Sham (at Day 1) will continue with monthly Sham injections through Month 23. All patients will have a final follow-up visit at Month 24. The trial consists of a total treatment period of 24 months. This SAP covers all analyses to be performed on Year 2 cumulative data.

1.3. Study Period and Visit Window Definition

Study assessments in Year 2 are summarized below.

Year 2

2. Statistical Hypotheses

The following hypothesis testing will be conducted sequentially.

1. Hypothesis testing in EM vs. Sham for mean GA growth rate are:

$$H_0: \Delta = 0$$

$$\text{versus } H_1: \Delta \neq 0,$$

where $\Delta = \mu_1 - \mu_2$, μ_i is the mean growth rate (slope) of GA over 24 months for treatment EM, or Sham, respectively.

2. Hypothesis testing in ACP 2mg vs Sham for time to vision loss will be conducted using Kaplan-Meier method with a log-rank test
3. Hypothesis testing in EOM vs. Sham for mean GA growth: similarly, as in (1)
4. Hypothesis testing in ACP 2mg vs Sham for mean change in best corrected visual acuity (BCVA in ETDRS letters) from Baseline to Month 24
5. Hypothesis testing in ACP 2mg vs Sham for mean change in low luminance best corrected visual acuity (LL BCVA in ETDRS letters) from Baseline to Month 24
6. CCI

The hypothesis testing will be evaluated according to a pre-specified hierarchical testing procedure to control overall type-1 error at a 5% two-sided significance level. If the primary analysis testing GA growth rate (ACP 2mg vs Sham) based on Year 1 data is statistically significant, the hypotheses tests will be performed in a sequential way as described above to control familywise type I error rate with 2-sided significance level of 0.05. A test will be performed only if all the preceding tests are statistically significant.

2.1. Multiplicity Adjustment

There will be no adjustment for the multiplicity as the hypotheses will be tested in a hierarchical procedure on the primary endpoint and the secondary endpoints described above.

3. Analysis Sets

For the purposes of analyses, the following analysis sets (populations) will be used and are defined below.

Participant Analysis Set (population)	Description
Intent-to-treat analysis set (ITT)	All randomized participants who received at least one dose of study drug. Participants will be analyzed in the treatment group assigned at randomization
Safety analysis set (Safety)	All participants who received at least one dose of study drug. Subjects who have ever received an injection of ACP during this trial will be analyzed in the ACP group.
Re-randomized analysis set (Re-Rand)	The subset of ITT population who are re-randomized at Month 12

In the ITT/Safety population, ACP (ARC1905 2mg) and Sham will be used as treatment groups. Subjects who were discontinued from the study in Year 1 will be included. In the Re-randomized population, ARC1905 2mg EM, ARC1905 2mg EOM, and Sham will be used as treatment groups. Subjects who were discontinued from the study in Year 1 will be excluded.

4. Statistical Analyses

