11.1 Study Design

This is a randomized, double-masked, Sham-controlled pivotal study that will obtain evidence regarding the effects of Zimura 2 mg in reducing the mean rate of GA growth over 12 months, when compared with Sham control.

Approximately 400 patients will be randomized at Day 1 in a 1:1 ratio to the following monthly treatment groups:

- Zimura 2 mg
- Sham

Patients receiving monthly Zimura 2 mg will be re-randomized at Month 12 in a 1:1 ratio to the following treatment groups:

- Zimura 2 mg administered monthly from Month 12 - Month 23
- Sham administered at Months 12, 14, 16, 18, 20, and 22, and Zimura 2 mg administered every other month at Months 13, 15, 17, 19, 21, and 23

All patients who were initially randomized to Sham (at Day 1) will continue with monthly Sham injections through Month 23.

All patients will have a final follow up visit at Month 24.

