4.2. Efficacy Analysis

4.2.1. Mean GA growth (slope): EM, EOM vs. Sham

4.2.1.1. Definition of Estimand

The objective is to demonstrate efficacy of ACP EM or EOM versus Sham in mean GA growth rate (slope) after re-randomization regardless of any non-adherence to or interruption of study treatment, and regardless of initiation of alternative treatment.

The following 5 attributes define the Estimand for the objective evaluation:

A. Population: re-randomized population

B. Interventions:

ACP EM or EOM versus Sham.

C. Endpoint:

GA area over 24 months from Baseline, Month 6, Month 12, Month 18, and Month 24.

D. Intercurrent events (ICE's) and strategies:

1. Treatment changes (i.e., interruptions, non-adherence, dose changes, discontinuation): “treatment policy” – i.e., treatment changes will be ignored, and all data collected will contribute to the analysis regardless of whether these follow such ICE's.
2. COVID-19: “treatment policy” – i.e., impact of COVID-19 pandemic will be ignored, and all data collected will contribute to the analysis regardless of whether these follow such ICE's.

E. Population-level summary:

Difference between groups (EM vs. Sham, EOM vs. Sham) in mean growth rate (slope) of the GA area over 24 months.

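### The EM and EOM versus Sham GA slopes are tested only on patients still in the study at Month 12, in an analysis set whose wording leaves out Sham

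*SAP*

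**What the plan says.** Year 2 SAP section 3 defines the Re-Rand set as "The subset of ITT population who are re-randomized at Month 12". It then names EM, EOM and Sham as the groups in that set and excludes patients who discontinued from the study in Year 1. That exclusion is one sentence and does not distinguish between arms.

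Only ACP patients are re-randomised. Protocol 11.1 says "Patients receiving monthly Zimura 2 mg will be re-randomized at Month 12 in a 1:1 ratio". For the control arm, Year 2 SAP section 1.2 says "All patients who were initially randomized to Sham (at Day 1) will continue with monthly Sham injections through Month 23".

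The estimand for the GA slope (Year 2 SAP 4.2.1.1) states "A. Population: re-randomized population" and takes GA area at Baseline and at Months 6, 12, 18 and 24. Section 4.1.7 analyses the set by re-randomised treatment, which a Sham patient does not have.

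Section 2 makes EM versus Sham the first Year 2 test and EOM versus Sham the third. The sequence opens "If the primary analysis testing GA growth rate (ACP 2mg vs Sham) based on Year 1 data is statistically significant", and after that "A test will be performed only if all the preceding tests are statistically significant". The stated purpose is "to control familywise type I error rate with 2-sided significance level of 0.05". Hypotheses 2, 4 and 5 use the ITT set (4.2.2.1, 4.2.3). Protocol 11.7.4 places the efficacy analysis on all randomised and treated patients.

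**The concern.** Whether a patient is still in the study at Month 12 is known only after a year of treatment or sham. Comparing those who remain, on a slope that includes that same year, conditions on an event that treatment could influence. If leavers progress differently from stayers, and do so unequally between arms, the difference in slopes is shifted.

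The missing-at-random argument in Year 2 SAP 4.1.2 does not help. It covers missing visits of patients who are in the model, whereas Year 1 leavers are removed before fitting, along with any Baseline and Month 6 readings.

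What is at stake is mainly hypothesis 1. A false pass opens the rest of the Year 2 hierarchy, and a false failure closes it. The literal definition adds a practical problem: a programmer cannot derive Sham membership from it.

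**Working it through.** **1. Who is in the set, and over what period**

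- Entry: re-randomised at Month 12 (Year 2 SAP 3). Sham is never re-randomised (1.2), yet Sham is listed as a group in the same section. The text does not agree with itself.
- Period: Baseline to Month 24 (4.2.1.1, and section 2 for hypothesis 1). Year 1 growth counts, but Year 1 leavers do not.
- Sensitivity analyses (4.2.1.3): Miller imputation, tipping point, categorical time, piece-wise slopes. None names the ITT set or brings the leavers back.

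**2. Is entry the same in each arm?**

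- Protocol 11.1 and Year 2 SAP 1.2 describe re-randomisation of patients receiving monthly drug.
- Protocol 11.5 and the Randomization section of the Year 1 SAP describe it for everyone allocated to Zimura on Day 1, with no on-treatment condition.
- The Year 1 SAP (procedures for minimizing missing data) expects patients to stay in follow-up after stopping treatment.

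The documents therefore do not settle whether an ACP patient who is off treatment but on study is re-randomised. If not, that patient is absent while a comparable Sham patient is kept.

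**3. The plan's own figure**

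Protocol 11.3 gives 97% power for 0.11 mm with about 200 per arm, and a significance threshold of 0.057 mm.

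- SE = 0.057/1.96 = 0.0291; SD = 0.0291/√(2/200) = 0.291 mm.
- Power = Φ(0.11/0.0291 − 1.96) = 96.6%, which reproduces the stated 97%.

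This is the Year 1 test on the 12-month square-root scale. Hypotheses 1 and 3 use untransformed area over 24 months (Year 2 SAP 4.2.1.2), for which no SD, power or dropout rate is visible. The steps below therefore stay in SD units of the slope.

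**4. Illustration of the bias (all dropout inputs are assumptions)**

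Let d be the share excluded and g the excess slope of excluded over retained patients, in SD, with T for ACP and S for Sham.

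- Bias in the ACP minus Sham slope, relative to all treated patients = −(d_T·g_T − d_S·g_S). A negative value favours ACP.
- SE = √(1/n_T + 1/n_S), with n_T = 100(1 − d_T) for EM and n_S = 200(1 − d_S).
- Size = Φ(−1.96 − bias/SE) + 1 − Φ(1.96 − bias/SE), when there is no true difference among all treated patients.

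| Excluded ACP / Sham | g ACP / Sham | Bias (SD) | Two-sided size |
|---|---|---|---|
| 10% / 10% | 0.5 / 0.5 | 0 | 5.0% |
| 20% / 10% | 0 / 0 | 0 | 5.0% |
| 15% / 10% | 0.5 / 0.5 | −0.025 | 5.4% |
| 20% / 10% | 0.5 / 0.5 | −0.05 | 6.6% |
| 15% / 15% | 0.5 / 0 | −0.075 | 8.7% |
| 20% / 10% | 1 / 1 | −0.10 | 11.5% |

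The sign can reverse. With 10% ACP and 15% Sham excluded and g = 0.5 in both arms, bias = −(0.10×0.5 − 0.15×0.5) = +0.025 SD, against ACP. Slower-growing leavers reverse it too.

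**5. The entry question alone**

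Assume a further 5% of ACP and of Sham leave the study without effect on slope. If 5% of patients are off treatment but on study, kept in Sham and absent from ACP, and grow 0.5 SD faster, the bias is −0.05×0.5 = −0.025 SD and the size 5.4%. With 10% and 1 SD it is −0.10 SD and 12%.

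**The case against.** The strongest defence is that the intended set is readable: patients still in the study at Month 12, in all three groups. Section 3 names Sham, and one clarifying sentence would close the gap. The estimand is also coherent on its face, since its objective is efficacy after re-randomisation and its population is chosen to match. A plain ITT test of EM versus Sham is impossible because Year 1 ACP leavers have no EM or EOM label. Their data are not lost to the trial: they enter the Year 1 primary model, and the addendum in section 5.2 keeps ACP leavers in an ACP-overall group.

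Most of this stands. It does not remove the core point, because the slope starts at Baseline and so is not confined to the period after re-randomisation.

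A reader might infer more than the documents support:

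- **That each arm has its own written exclusion rule.** The only exclusion sentence covers all groups. A difference in entry is possible but unsettled (step 2 of the working).
- **That the population contradicts the treatment-policy strategy.** That strategy governs intercurrent events within the chosen population and does not decide who belongs to it.
- **That these are non-randomised comparisons.** ACP and Sham were randomised on Day 1, and EM versus EOM at Month 12. What is lost is full protection.
- **That this is the first gate of the whole sequence.** The Year 1 primary test, on ITT, comes before it.

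**Conclusion.** The point holds in this form. Hypotheses 1 and 3 compare Month 12 stayers on a slope that begins at Baseline. Year 1 leavers are removed before the model is fitted, and nothing in the listed sensitivity analyses shows what that does to the result. This departs from protocol 11.7.4 and from the ITT basis of hypotheses 2, 4 and 5. Separately, the literal definition has no Sham patients, and the status of on-study, off-treatment ACP patients is left open.

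The size cannot be stated from the documents. On assumed inputs the effect runs from none, through a two-sided size of 5.4% to 8.7% in moderate cases, to 11.5% or 12% in strong ones. These figures use a normal approximation with one slope per patient and equal SDs. A reader might take the table as evidence of a bias towards ACP. It is not: the dropout rates and leaver profiles are invented for illustration, and the sign reverses with them. Nor should the figures be turned into a share of the 0.11 mm design effect, which belongs to a different scale and period.

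**What to change.** 1. **Define entry once.** State one Month 12 on-study criterion for the Re-Rand set, applied identically to EM, EOM and Sham and regardless of treatment status. Reconcile Protocol 11.1 and Year 2 SAP 1.2 with Protocol 11.5 on who is re-randomised. Report exclusions by arm, with reasons and last available GA growth.
2. **Keep all treated Day 1 patients in the GA slope analysis.** Fit one shared ACP segment to Month 12 and separate EM and EOM segments afterwards, against all Sham patients. With two 12-month segments, the EM contrast is ½[(ACP − Sham slope, Months 0–12) + (EM − Sham slope, Months 12–24)], and likewise for EOM. State how on-study ACP patients who were never re-randomised enter after Month 12. One option is to count them under both regimens and give re-randomised patients weight 2. Keep the Re-Rand analysis as supportive.
3. **At minimum,** add a 24-month GA slope of all ACP versus Sham on the ITT set as a sensitivity analysis, and list the choice of population in section 4.5.

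The cost is SAP wording and one model specification. No new data are needed. The contrast is slightly more complex than a single slope, and the Year 2 segments still rest on missing at random.
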